6.6. Screening Procedures

Two screening strategies will be adopted:

- a) Patients with suspected pulmonary TB or confirmed *M.tb* positive (< 5 days since treatment initiation) will be screened and consented to provide an additional sputum sample for Xpert MTB/XDR testing *if required*. This will be *based on* the routine sample collected for any currently available Nucleic Acid Amplification Tests for drug-resistance detection changes
- b) We will concurrently contact all patients with newly identified RR-TB during the study enrolment period directly for participation in this study (laboratory records)

The site investigator (or designate) will assess eligibility and ensure that the participant meets study inclusion criteria. Xpert MTB/XDR (Cepheid) will be implemented as an additional DR-TB screening test. All participants must test positive for *M.tb* and participants with RR-TB will be screened for additional resistance and enrolled in Cohort 1 (estimated n=880) while those without RR will be screened for isoniazid resistance and enrolled in Cohort 2. Participants with HR-TB will be enrolled in Cohort 2 (estimated n=400). As this is an operational study, accrual

into the study will be within a specified time frame. Overview of screening and enrolment approach is outlined in figure 3.

[figure not shown]

Figure 3: Study screening and enrolment for the TRIAD Study

6.7. Enrolment Procedures

Study staff will contact potential participants meeting eligibility criteria, based on the Xpert XDR test, for study enrolment. Participants will be re-assessed for their willingness to participate in the study. Participant accrual at all sites will occur over 12 -18 months from the date of enrolment of the first participant.

Participants will be given further information about the study. Ineligible participants will be referred to the National Tuberculosis Programme (NTP) for further management. Eligible

participants who agree to study participation will undergo study informed consent procedures (signature or give a thumb print in the presence of a witness if illiterate). Enrolled participants will be given a signed copy to take home.

After obtaining study informed consent, clinical research sites will:

- Obtain consent from participants for sputum sample storage and further analysis
- Record participant contact information including physical address
- Interview participants to obtain demographic details, medical history (including all prior TB diagnoses, history of previous TB drug intake)
- Conduct a targeted clinical examination

7. STUDY ASSESSMENTS AND FOLLOW-UP

7.1. Schedule of evaluations

The sequence of study visits and procedure schedules are presented in tables 3 and 4 schedule of evaluations for cohort 1 and 2, respectively. These tables detail visit requirements for each in-person follow-up visit. Each follow-up visit will include collection of a sputum sample, a clinical examination and assessment for adverse drug reactions. Study staff will be trained to conduct study procedures in a standardised manner. Study specific standard operating procedures (SOPs) will guide this process.

Screening (Cohorts 1 and 2):

Screening will include the provision of introductory study information, assessment of eligibility criteria and obtaining written informed consent for screening procedures. Participants who meet the eligibility criteria will provide up to two sputum samples for currently available Nucleic Acid Amplification Tests for drug-resistance detection and Xpert XDR testing. For potential participants who do not meet the study eligibility criteria, the screening process will be discontinued when ineligibility is determined.

Evaluations for Cohort 1:

Participants will be scheduled to undergo appropriate evaluation at baseline, during and after treatment. Study visits will occur at week 2, monthly for the duration of DR-TB treatment and 3-monthly following completion of treatment where allowable within the study's operational time frame. Participants on short-regimen will be seen for a maximum of 3 post-TB treatment visits, 3 months apart (Table 3). Active follow-up will occur for the duration of TB treatment and passively thereafter, for a maximum of 18 months after study enrolment. Participants who receive long treatment regimens will be actively followed-up for the duration of the intensive phase of treatment and passively thereafter to obtain an end-of-treatment outcome. Research-specific activities during follow-up include assessment of clinical and microbiological response to treatment, solicitation and reporting of adverse events and serious adverse events, administration of study specific questionnaires related to costs, acceptability and feasibility of the intervention. Passive follow-up will be conducted telephonically or through NTP registers to assess rates of relapse after TB treatment completion. Study related specimen collection will occur at baseline (enrolment) and at all follow-up visits. Baseline sputum samples will be collected for Xpert MTB/XDR testing, pDST, WGS, and TB-MBLA testing. Follow-up sputum samples will be collected for routine culture and susceptibility testing and sputum storage for batched TB-MBLA testing.

Evaluations for Cohort 2:

Participants will be referred to the NTP and will not undergo further active follow-up within the study (table 4). Treatment outcomes for these participants will be monitored passively through monthly telephonic monitoring or through routinely collected outcome data within the national TB program until 15 months after enrolment.

Table 3: Schedule of Evaluation for Drug-Resistant Tuberculosis participants in the TRiAD Study Cohort 1

Visit	Screening	Enrolment	24h after 1 st treatment dose	Treatment and Follow Up Period ^a											
				Week 2	Month 1	Month 2	Month 3	Month 4	Month 5	Month 6	Month 9	Month 12	Month 15	Month 18	
Time of visit															
Inclusion/Exclusion Criteria	X	X													
Informed Consent	X	X													
Storage informed consent ^g		X													
Sociodemographic Information		X													
Medical/treatment History ^b		X													
Clinical Exam ^c		X		X	X	X	X	X	X	X	X	X	X	X	X
TB Symptom Profile	X	X		X	X	X	X	X	X	X	X	X	X	X	X
Peripheral Neuropathy Assessment		X		X	X	X	X	X	X	X	X	X	X*	X	
ECG monitoring		X		X	X	X	X	X	X	X	X	X	X	X	X
Chest X-Ray ^d		X						X			X		X		
Laboratory Safety Assessments ^e		X		X	X	X	X	X	X	X	X	X	X	X	X
Sputum Sampling ^f	X	X		X	X	X	X	X	X	X	X	X	X	X	X
Blood sampling (1x4ml EDTA Tube) ^h		X					X							X	

Spot Urine collection sample (approximately 30ml) ⁱ		X											
Self -collection urine sample (approximately 5L) ^j			X								X		
Participant Questionnaire ^k		X											
Solicited Adverse Events (AES)/SAE ^l			X	X	X	X	X	X	X	X			

Notes:

- a. **Treatment and follow-up:** Active follow-up will occur during TB treatment only, passive follow-up visits up to 18 months post-TB treatment, no specimen collection during passive follow-up. Visits for month 12 onwards applicable to participants who continue treatment for longer than 6 months only. Passive follow-up visits will collect AE's, SAE's, verification of survival and participant reported TB outcome information. These will be conducted telephonically
- b. **Medical History:** will include TB treatment history, HIV/Status and CD4 and Viral load Monitoring: If HIV status is unknown or reported negative in the absence of documentation, HIV test should be requested. CD4 and Viral load test to be conducted for all HIV-positive participants as per standard of care
- c. **Clinical Exam:** will include random blood glucose test, ophthalmic examination of visual acuity and colour vision assessment, pregnancy test will be conducted in women of child-bearing potential and peripheral neuropathy assessment
- d. **Chest X-Ray:** Will be conducted at screening visit, month 4 (South African standard of care) and thereafter at the request of the treating clinician if deemed necessary. In Nigeria, X-rays will be done at screening visit, month 4 and end of treatment
- e. **Laboratory Safety Assessments:** Haematology, full blood count, clinical chemistry and urinalysis - as per routine in-country standard of care
- f. **Sputum Sampling:** 1 sample will be collected at baseline/screening: for currently available Nucleic Acid Amplification Tests for drug-resistance detection, routine culture and Xpert XDR testing, *an additional sample will be requested if required*, 2 samples will be collected at enrolment: storage for TB-MBLA and WGS/MIC testing
- g. Optional Storage Consent for additional sampling collection and storage: Subset of participants who are willing to consent to provision of urine and blood samples at enrolment, month 3, the end of TB treatment, and 6 months post treatment completion if still in follow up, will be required to provide written consent

- h. **Optional Blood Sampling:** # Subset of participants to provide samples to be collected at enrolment, month 3, at the end of TB treatment, and 6 months post treatment completion if participant still in follow up
- i. **Optional Spot Urine Collection Sample:** **Subset of participants to provide** pre-treatment spot urine collection to be conducted during the enrolment visit
- j. **Optional Self-collection of Urine Sample:** **Subset of** participants to collect a 24-hour urine sample following first dose of TB treatment and another 24-hour self-collection urine sample at month 6 after treatment initiation
- k. **Participant Questionnaire:** assess participant associated costs and acceptability of study approach; schedule for administration to be finalised with sub-study protocol
 - I. **Reporting of adverse events:** record solicited grade 3 and 4 adverse events during treatment phase only and all serious adverse events throughout study follow-up.

Table 4 : Schedule of Evaluation for Drug-Resistant Tuberculosis participants in the TRiAD Study Cohort 2

Visit	Screening	Enrolment	Treatment and Follow Up Period ^a											
			Week 2	Month 1	Month 2	Month 3	Month 4	Month 5	Month 6	Month 9	Month 12	Month 15		
Time of visit														
Inclusion/Exclusion Criteria	X	X												
Informed Consent	X	X												
Sociodemographic Information		X												
Medical/treatment History		X												
Clinical Exam		X												
TB Symptom Profile		X												
ECG monitoring		X												
Chest X-Ray ^b		X												
Sputum Sampling ^c	X	X		X	X	X	X	X	X	X	X	X		
Telephonic Assessment														

Notes:

- Treatment and follow-up:** Passive follow-up visits up to 6 months post-TB treatment, routine monitoring of treatment response. Passive follow-up visits will collect AE's, SAE's, verification of survival and participant reported TB outcome information. These will be conducted telephonically
- Chest X-Ray:** Will be conducted at screening visit, and thereafter at the request of the treating clinician if deemed necessary. In Nigeria, X-rays will be done at screening visit, month 4 and end of treatment
- Sputum Sampling:** 1 sample will be collected at baseline/screening: for any currently available Nucleic Acid Amplification Tests for drug-resistance detection and Xpert XDR testing, an additional sample will be collected if required.

1 sample will be collected at enrolment: for culture and storage for WGS/MIC testing

The study SoE will be followed except when procedures are clinically indicated or not in accordance with clinical judgement.

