6.2. Selection of Participants

Approximately 4800 participants will be screened across the 13 sites (in South Africa, Nigeria and Ethiopia) to enrol 1280 eligible participants. All presumptive TB patients presenting for diagnosis at the study sites will be approached for screening. Each of the sites will also contribute to the historical cohort as described below.

6.2.1. Selection of cohort 1

880 RR-TB (n=440 in SA, n=220 in Nigeria and n=220 in Ethiopia) participants will be enrolled into Cohort 1. Each participant in cohort 1 will be followed up for the duration of TB treatment and passively thereafter to a maximum of 18 months from TB treatment initiation.

6.2.2. Selection of cohort 2

400 HR participants into Cohort 2 (n=200 in SA, n=100 in Nigeria and Ethiopia). Each participant in cohort 2 will be followed up passively for the duration of TB treatment and passively thereafter to a maximum of six months.

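### Section 7.1 ends active follow-up of long-regimen Cohort 1 participants at the intensive phase, while section 6.2.1 and Table 3 keep it through treatment; the 18-month follow-up limit also has three different starting points

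*Protocol*

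**What the plan says.** Five places in the protocol bear on how long a Cohort 1 participant is actively followed.

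- **Section 7.1, Evaluations for Cohort 1, general rule:** "Active follow-up will occur for the duration of TB treatment and passively thereafter, for a maximum of 18 months after study enrolment".
- **Section 7.1, same paragraph, long regimens:** "Participants who receive long treatment regimens will be actively followed-up for the duration of the intensive phase of treatment and passively thereafter". The stated aim is an end-of-treatment outcome.
- **Section 6.2.1:** each Cohort 1 participant is to be "followed up for the duration of TB treatment and passively thereafter to a maximum of 18 months from TB treatment initiation".
- **Table 3, note a:** "Active follow-up will occur during TB treatment only", then "passive follow-up visits up to 18 months post-TB treatment, no specimen collection during passive follow-up". On the late columns it says: "Visits for month 12 onwards applicable to participants who continue treatment for longer than 6 months only". Passive contacts are by telephone and collect AEs, SAEs, "verification of survival and participant reported TB outcome information".
- **Section 7.1, opening, on Tables 3 and 4:** "These tables detail visit requirements for each in-person follow-up visit". After Table 4 the protocol adds that the schedule is to be followed unless clinical indication or judgement says otherwise.

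Table 3 marks clinical examination, ECG, laboratory safety tests and sputum at months 9, 12, 15 and 18. As extracted, its solicited adverse event row stops at month 6, whereas note l has solicited grade 3 and 4 events recorded throughout the treatment phase.

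**The concern.** The long-regimen sentence in section 7.1 makes these participants passive for most of their course. The other places keep them active until treatment ends. ECGs and sputum cannot be obtained by telephone, so the two instructions cannot both be carried out, and sites may choose differently.

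Two kinds of study data depend on the choice.

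- **Safety.** Every long regimen that Table 2 sets out in phases continues linezolid after the first block. The linezolid entry in Table 9 advises monthly blood counts once past the initial period, monthly neuropathy checks and visual tests every two months. Section 9.2 reports adverse events by regimen, so ascertainment would differ by regimen and by how each site reads the rule.
- **Bacteriology.** The TRiAD column of Table 7 requires at least three negative cultures after the intensive phase for cure, and it names reversion in the continuation phase among the reasons for failure. Note a allows no study specimens in passive follow-up.

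The follow-up limit matters separately. If it expires before treatment does, the end-of-treatment outcome that section 7.1 seeks falls outside follow-up.

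**Working it through.** The protocol gives no visit total to reproduce, so the check counts scheduled visits under each rule.

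**Inputs**

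- Post-baseline visit columns in the Table 3 header: week 2, months 1 to 6, then months 9, 12, 15 and 18. The extracted procedure rows hold one more cell than the header has columns. This is a conversion artefact, so the count uses the header.
- Long regimens in Table 2, current-practice column: 6 + 12 = 18 months (South Africa, Nigeria); 6 + 14 = 20 months (Ethiopia); South African individualised regimen 6 to 8 + 12 = 18 to 20 months.
- Assumption: the first block in Table 2 is the intensive phase.
- Section 7.2: one sputum sample for smear and culture at each visit.

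**In-person visits after month 6, on the Table 3 grid**

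| Intensive phase | Section 7.1 long-regimen sentence | Table 3 through treatment |
|---|---|---|
| 6 months | 0 | 4 (months 9, 12, 15, 18) |
| 8 months | 0 (no column between months 6 and 9) | 4 |

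The result is the same for 18-month and 20-month courses, because the last column is month 18.

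**Study-visit cultures after the intensive phase:** 0 under the long-regimen sentence with note a, and 4 under the grid. The TRiAD definition of cure asks for 3.

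**Treatment time outside active follow-up under the long-regimen sentence:** 12 of 18 months (67%), 14 of 20 (70%), or 12 of 20 (60%).

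**Follow-up limit for a 20-month course**

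- From treatment initiation (section 6.2.1): 18 − 20 = −2, so it ends 2 months before treatment does.
- From enrolment (section 7.1): also about 2 months short, if treatment starts close to enrolment.
- After treatment (note a): 20 + 18 = month 38.

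**Room for a longer limit:** with 12 to 18 months of accrual, a participant enrolled last on a 20-month course finishes 12 + 20 = 32 to 18 + 20 = 38 months after the first enrolment. The study lasts 48 months.

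**The case against.** The best defence is that a specific sentence qualifies a general one. Within section 7.1 the long-regimen sentence follows directly on the general rule and gives its own purpose, so it reads as a deliberate exception. Section 6.2.1 is a short summary that gives no visit schedule and does not use the word active. Section 8.2 also provides passive follow-up, at reduced frequency if needed, for people whose study treatment is stopped or changed.

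This resolves section 7.1 internally but not the rest. Section 6.2.1 speaks of each Cohort 1 participant and makes follow-up passive only after treatment. Note a keeps follow-up active during treatment and assigns the month 12 and later visits to people treated beyond 6 months, which includes every long regimen. Section 8.2 narrows the problem mainly to those who start on a long regimen.

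Several objections to the consequences do stand.

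- Table 5 lists follow-up culture as routine testing, and section 7.1 lets passive follow-up use programme registers. A reader might infer that cure could never be shown. The documents do not support that: programme cultures may exist, though the protocol does not say they are abstracted for these participants, as section 6.2.3 does for the historical cohort.
- A reader might infer that a missed reversion turns a failure into a success. Table 7 failure also needs treatment to be terminated or at least two drugs to be changed permanently, and registers or telephone contact could reveal that.
- A move from cured to completed leaves treatment success unchanged. The 2021/2022 WHO column does not ask for three cultures. The second primary objective is set at month 12, before an 18- to 20-month course ends.
- The monthly-visit sentence in section 7.1 would give other counts, but mixing it with the grid compares two different schedules. The figures here use the grid alone.
- Read literally, the post-treatment limit in note a could carry late enrolees past 48 months. Table 3 stops at month 18 and section 7.1 caps follow-up at 18 months after enrolment, so a planned overrun does not follow.

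**Conclusion.** The contradiction is real and affects how sites would run the study. For long-regimen participants the protocol prescribes either 0 or 4 in-person study visits after month 6, depending on which section is followed. What is chiefly at risk is in-person safety information during 12 to 14 months of continuation-phase linezolid. Study-visit cultures that support the split between cured and completed and help detect reversion are also at risk. The issue is the completeness of study data; programme care and telephone collection of AEs and SAEs continue.

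Any effect on combined treatment success is uncertain in size and direction, and time to treatment initiation is unaffected. The number of participants concerned is not given. It is probably small, because Table 2 proposes BPaL for both long-regimen rows. The visit counts rest on the Table 3 header and on taking the first Table 2 block as the intensive phase.

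Two related inconsistencies belong to the same correction: the solicited adverse event row ends at month 6 although note l covers the whole treatment phase, and the 18-month limit has three starting points, two of which end about 2 months before a 20-month course. This should be fixed, because it determines what is collected and is cheap to put right.

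**What to change.** State one rule in sections 6.2.1 and 7.1 and in Table 3 (notes a and l, and the solicited adverse event row).

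- **Preferred:** keep the existing in-person visits at months 9, 12, 15 and 18 for anyone still on treatment, and extend the solicited adverse event row to match note l.
- **Alternative:** if continuation-phase monitoring passes to the national programme, write the long-regimen exception into note a and section 6.2.1. Sites should then abstract programme blood count, neuropathy, visual and culture results into the CRF to the end of treatment.

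Use one follow-up limit with one starting point in all three places, long enough to reach the end of a 20-month course and contained within the 48-month study. The clinical monitoring frequency is for the investigators to settle.

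The first option changes protocol wording only, since the visit columns already exist. The second adds modest data entry for what is probably a small number of participants.

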8.2. Discontinuation of treatment due to toxicity or treatment failure

The study regimens will be discontinued in some participants. In such cases, participants will be evaluated by the MMT and switched to an individualized regimen, based on the WHO guidelines for regimen design. The most common situations in which the regimen may be discontinued include:

- **Intolerable severe toxicity.** One or more drugs may need to be suspended permanently due to severe toxicity. In such cases, the clinical committee should review the medical history carefully to determine how the regimen should be modified (see discontinuation/modification criterion below).
- **Treatment failure.** If clinical and bacteriological responses to treatment are poor, a change in the treatment regimen should be considered. DST should be repeated if culture is still positive at month 4, whether or not the regimen is changed, in order to inform future management decisions.
- **Resistance to drugs in the regimen.** For participants who submit a sputum sample for culture-based second-line DST at the beginning of treatment, results may not be available until after treatment has started. If resistance to component drugs is discovered after treatment is initiated, it may be necessary to modify, extend treatment duration or discontinue the regimen.
- **Pregnancy during treatment.** For participants who become pregnant during treatment, it may be advisable to modify or discontinue novel regimens. A decision regarding continuation or discontinuation of the regimen should be made after a review by the study MMT and discussion with the participant

For participants discontinued from study treatment or whose treatment is changed and participants referred to the NTP, every effort should be made to continue passive follow up (at a reduced frequency if necessary), unless the participant has specifically withdrawn consent for further follow-up. In this event, a final status form should be completed. Details for management these participants will be outlined in a study specific SOP.

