9.3. Outcome Status

Outcomes are based on WHO's reporting framework for tuberculosis in 2020 (39).Treatment outcome definitions have recently been revised by WHO and will be updated in the 2021 revision of WHO's *Definitions and reporting framework for tuberculosis*. Once this guideline becomes available and the new definitions are adopted for programmatic implementation, the protocol will be updated (<https://www.who.int/publications/i/item/9789240022195>).

Table 7: Treatment outcomes for RR-TB/MDR-TB/XDR-TB participants treated

Outcome	Definitions per TRiAD Protocol	2021/2022 WHO Definitions
Cured	Treatment completed as recommended by the national policy without evidence of failure AND three or more consecutive cultures taken at least 30 days apart are negative after the intensive phase	A pulmonary patient with bacteriologically confirmed DR-TB at the beginning of treatment who completed the recommended treatment , with evidence of bacteriological response* and no evidence of failure
Treatment completed	Treatment completed as recommended by the national policy without evidence of failure BUT no record that three or more consecutive cultures taken at least 30 days apart are negative after the intensive phase	A patient who completed treatment as recommended and who does not meet the definition of cure or treatment failure
Treatment failed *	Treatment terminated or need for permanent regimen change of at least two anti-TB drugs because of: 
 - lack of conversion by the end of the intensive phase, or - bacteriological reversion in the continuation phase after conversion to negative, or - evidence of additional acquired resistance to fluoroquinolones or second-line injectable drugs, or - adverse drug reactions (ADRs) 	A patient whose treatment regimen needed to be terminated or permanently changed to new regimen or treatment strategy. Reasons for change include : 
 - No clinical and or bacteriological response - Adverse drug reaction/s - Evidence of additional drug resistance to medicines in the regimen
Died	A participant who dies for any reason during the course of treatment.	A patient who died for any reason during treatment
Lost to follow-up	A participant whose treatment was interrupted for 2 consecutive months or more.	A patient with treatment interrupted for ≥ 2 consecutive months for any reason without medical approval

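### Sections 7.1 and 8.2 and Table 3 note a disagree on whether cohort 1 participants still on treatment keep sputum culture, so a late reversion can go unrecorded and count as Treatment completed

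*Protocol*

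**What the plan says.** **Rules that keep follow-up active.** Section 7.1 sets monthly visits throughout DR-TB treatment and makes follow-up passive only afterwards. Table 3 note a agrees: "Active follow-up will occur during TB treatment only". The note reserves the visits from month 12 for people treated beyond 6 months, and the Table 3 sputum row is marked through to month 18.

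**Rules that make it passive earlier.** Section 7.1 also says that participants on long regimens are "actively followed-up for the duration of the intensive phase of treatment and passively thereafter to obtain an end-of-treatment outcome". For people whose treatment is discontinued or changed, or who are referred to the national programme (NTP), section 8.2 says "every effort should be made to continue passive follow up (at a reduced frequency if necessary"), unless consent is withdrawn.

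**What passive follow-up contains.** Note a specifies "no specimen collection during passive follow-up" and adds: "Passive follow-up visits will collect AE's, SAE's, verification of survival and participant reported TB outcome information", by telephone. Section 7.1 is slightly wider: "Passive follow-up will be conducted telephonically or through NTP registers". That sentence, however, concerns relapse after treatment has been completed.

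**What the outcome needs.** Under the protocol column of Table 7 (section 9.3), one ground for failure is "bacteriological reversion in the continuation phase after conversion to negative". Reversion means two consecutive positive cultures at least 30 days apart. Cured needs three negative cultures after the intensive phase. Treatment completed takes a participant who finishes with no evidence of failure and no record of those three cultures. Treatment success is the sum of the two.

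**Historical cohort.** Section 6.2.3 has on-treatment bacteriological results, with dates, abstracted onto a CRF where relevant.

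**The concern.** Two sites could handle the same participant differently and both comply with the protocol. One would keep taking sputum to the end of treatment; the other would telephone.

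At the second site, a reversion after the intensive phase leaves no study culture, and a participant cannot report a culture reversion by telephone. Table 7 does not require evidence that failure is absent. It requires only that there be no evidence of failure, so missing cultures lead by default to Treatment completed. That category is part of the second primary outcome.

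The participants affected are those on long regimens or with a changed regimen, where toxicity, resistance or poor response is more likely. The stated data sources also differ between the groups compared: bacteriological results are abstracted for historical controls, while note a names a participant-reported outcome for passive cohort 1 participants. Time to culture conversion, a secondary outcome, is also cut short for anyone not yet converted when cultures stop.

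**Working it through.** The protocol states no figure for this point, so there is nothing to reproduce. The check compares the rules and then bounds the effect under stated assumptions.

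**Step 1: the rules compared**

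| Participant still on treatment | Passive from | Text pointing the other way |
|---|---|---|
| Long regimen | End of intensive phase (7.1) | 7.1 monthly visits; note a; Table 3 sputum to month 18 |
| Regimen stopped or changed | The change (8.2) | 7.1 and note a, if a new regimen is being taken |

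**Step 2: which failures could be missed.** The failure grounds in the protocol column of Table 7, taken in turn:

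- Termination, or a permanent change of at least two drugs, for a listed reason: already failure when it happens. Later cultures are not needed.
- Non-conversion by the end of the intensive phase: mostly seen during active follow-up. One gap is possible. Where a programme sets no maximum intensive phase, the Table 7 footnote uses 8 months, while the long regimens in Table 2 change at month 6.
- Reversion, or further acquired resistance, in the continuation phase: needs cultures after follow-up has turned passive.
- Changes under 8.2 that do not meet the failure definition, such as a single-drug change, pregnancy, or baseline resistance found late: these participants can still be classed as successes, and a later reversion needs cultures.

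The exposed groups are therefore the last two.

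**Step 3: how long the gap could be.** Table 2 gives long regimens of 6 + 12 months (South Africa, Nigeria) and 6 + 14 months (Ethiopia). Taking the first part as the intensive phase:

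- 12 / 18 = 67%
- 14 / 20 = 70%

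These durations come from the current-practice column. The proposed-regimen column replaces those rows with BPaL, so how many cohort 1 participants follow a long regimen is unknown.

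**Step 4: size.** Overstatement of the favourable proportion = (share on the passive route while treated) × (share of these failing after study cultures stop) × (share of those failures missed). The protocol gives none of the three. Assumed ranges are 5–30%, 2–10% and 50–100%.

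| Share | Late failure | Missed | Points |
|---|---|---|---|
| 0.05 | 0.02 | 0.5 | 0.05 |
| 0.10 | 0.05 | 1.0 | 0.5 |
| 0.20 | 0.10 | 0.5 | 1.0 |
| 0.30 | 0.10 | 1.0 | 3.0 |

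Of 880 participants, the extremes are 0.0005 × 880 ≈ 0.4 and 0.03 × 880 ≈ 26. The design difference in section 9.1 is 85% − 74% = 11 points.

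**Step 5: timing.** The primary objective (4.3) refers to month 12; the outcome measure (4.5) points to 9.3 without a time. Someone on an 18- or 20-month regimen from the start has not completed it at month 12 and so cannot be falsely favourable then. On that reading the error falls mainly on the end-of-treatment outcome.

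**The case against.** The strongest reply is that little is lost. Most changes of two or more drugs are failures already under Table 7, and its second column, the 2021/2022 WHO definitions, is wider still. Non-conversion is mostly seen while follow-up is active. A cure recorded as a completion leaves the endpoint unchanged. Section 7.2 describes culture as standard practice, and Table 5 lists follow-up culture under routine testing, so note a stops study specimens and not necessarily all cultures. Not evaluated is available when no outcome can be assigned. Section 8.2 leaves the management of discontinued or changed participants to an SOP that is not shown. The long-regimen sentence in 7.1 can also be read as an exception to a general rule.

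Most of this stands, and it narrows the point. It does not remove it:

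- Section 7.2 ties culture to visits, and no section requires routine results to be recorded for passive cohort 1 participants.
- The register sentence in 7.1 is about relapse after completion, not failure during treatment.
- The exception reading does not explain why Table 3 marks sputum to month 18 for people treated beyond 6 months.

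A reader might infer that failures in these participants are, in general, recorded as completions. The documents do not support that, because Table 7 catches most of them earlier. A reader might also infer a clean contrast between culture-informed controls and self-reported cohort 1 outcomes. Section 6.2.3 collects only what routine records hold, which need not include late cultures. If those are missing for controls too, the net bias is smaller than the figures above.

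**Conclusion.** The contradiction is in the text and bears on how a primary outcome is ascertained. Where the passive rules are followed, late reversions on long regimens, and after changes that are not already failures under Table 7, can be counted as favourable.

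In cohort 1 the error can only raise the favourable proportion. Its net effect on the comparison also depends on how complete the historical records are, which the documents do not say. The size cannot be fixed from the documents: about 0.05 to 3 percentage points under the assumed ranges, with the upper end needing all three assumptions at their maximum. The 67–70% describes the possible length of the gap for a participant on a Table 2 long regimen and should not be read as the share of outcomes affected.

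**What to change.** Reconcile 7.1, 8.2 and Table 3 note a into one data-collection rule for cohort 1 participants still on treatment, covering the period after the intensive phase of a long regimen and after a regimen change or NTP referral. Which visits take place is for the sponsor to settle; the outcome data should not depend on it.

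At minimum:

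- For every cohort 1 participant in passive follow-up while on treatment, abstract routine NTP culture results and dates onto the CRF to end of treatment, as for the historical cohort.
- State in 9.3 that a participant-reported outcome alone does not support Treatment completed. Without a programme record or culture result, the outcome is Not evaluated.
- Align note a with 7.1 by naming programme registers and laboratory records as sources for the outcome during treatment.

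The cost is wording in four places and some extra abstraction for the affected participants, using a method already planned for the controls. The favourable proportion in cohort 1 may come out slightly lower. Keeping the Table 3 sputum visits instead would give better data but adds visits for people whom 7.1 and 8.2 now make passive.
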